7.5 Follow-up of Unresolved Adverse Events

All AEs should be followed until they are resolved or the Investigator assesses them as chronic or stable or the subject's participation in the trial ends (i.e., until a final report is completed for that subject). Instructions for reporting changes in an ongoing AE during a subject's participation in the trial are provided in the instructions that accompany the AE CRFs.

In addition, all SAEs and those non-SAEs assessed by the Investigator as possibly related to the investigational medication/product should continue to be followed even after the subject's participation in the trial is over. Such events should be followed until they resolve or until the Investigator assesses them as "chronic" or "stable." Resolution of such events is to be documented on the appropriate CRF.

8. STATISTICAL CONSIDERATIONS

8.1 Data Management

Data from the study will be entered into eCRFs. Data may only be entered by authorized personnel. The data will be periodically monitored by the clinical monitor; in addition, programmatic edit checks will review the data for correctness, logic and consistency. Based on the monitoring findings and the edit checks, queries may be issued to the clinical site for data clarification. The results of all original entries, as well as any corrections, will be maintained by the data management system. The principal investigator will review and approve all data entries with electronic signature on the eCRF.

8.2 Study Design

A multi-arm, multi-institutional phase II study design will be used to assess the efficacy of Sacituzumab Govitecan in subjects with metastatic CRPC progressing on an ARSI. Patients will continue treatment on the ARSI and enroll on this trial. Prior exposure and sensitivity to second generation AR-directed therapy will be recorded and subjects will be considered to have responded (i.e., were sensitive) to the prior agent if there was a $\geq 50\%$ PSA decline from baseline.

Treatments can continue until radiographic disease progression, unacceptable toxicity, initiation of alternative therapy or withdrawal of consent.

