4. ENROLLMENT PLAN

Enrolled Subjects must have CRPC and have demonstrated disease progression (objective or PSA) while on second generation AR-directed therapy and have rising PSA levels immediately prior to enrollment based upon the criteria as defined by the PCWG2. PSA values must exhibit a rise on two occasions of at least a week apart, over a baseline value, with the final value ≥ 2 ng/ml. A graphical depiction of this is shown in **Figure 1** (PCWG2 Rising PSA Study Eligibility Criteria).⁶⁸

Prior exposure and sensitivity to AR-directed therapy will be recorded and subjects will be considered to have responded (i.e., were sensitive) to the prior agent if there was a $\geq 50\%$ PSA decline from baseline. Patients will continue on an ARSI and Sacituzumab Govitecan will be added to the treatment regimen as described below. Treatment with Sacituzumab Govitecan can continue until disease progression, unacceptable toxicity, initiation of alternative therapy or withdrawal of consent.

Figure 1. PCWG2 rising PSA study eligibility criteria

The reference value (#1) is the last PSA measured before increases are documented, with subsequent values obtained a minimum of 1 week apart. If the PSA at time point 3 (value #3A) is greater than that at point 2, then eligibility has been met. If the PSA is not greater than point 2 (value #3B), but value #4 is, the subject is eligible assuming that other criteria are met. Values 3A or #4 must be 2 ng/mL or higher.⁶⁸

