ECOG performance status assessments (Appendix A) are required to assess subject functional status for study eligibility purposes and will be performed throughout the study according to the schedule of procedures.

5.2.7 *ECG*

A 12-lead ECG will be obtained at screening and at the end of study visit. It is not necessary to do ECGs 5 minutes apart. Additional unscheduled 12-lead ECG may be conducted when necessary at the investigator's discretion.

5.3 *Determination of Extent of Metastatic Disease*

All subjects will undergo an extent of disease evaluation consisting of bone scintigraphy, CT of the chest, CT of the abdomen and pelvis, and other regions of known/suspected involvement, at Screening unless already conducted within 30 days of Cycle 1, Day 1. CT scans should be performed with contrast unless contraindicated. MRI abdomen and pelvis with contrast may be done in situations where a CT with contrast is equivocal or contraindicated. A non-contrast chest CT should be done for subjects requiring an MRI of the abdomen and pelvis.

Subjects will undergo repeat evaluations of their extent of disease every 9 weeks (\pm 7 days) if they remain progression- free on study. Imaging modality should remain consistent by lesion throughout the study.

5.4 *Laboratory Evaluations*

On treatment days, blood samples should be collected prior to infusion. Laboratory tests will be performed by local labs and will include:

5.4.1 *CBC*

A CBC will consist of determinations of hemoglobin (HGB), hematocrit (HCT), white blood cells (WBC), red blood cells (RBC), neutrophils, lymphocytes, monocytes, eosinophils, basophils, and platelet count. Absolute values are preferred.

5.4.2 *Coagulation factors*

Partial thromboplastin time (PTT) and prothrombin time (PT) or international normalized ratio (INR) will be obtained according to the schedule of procedures and at any other visit where clinically indicated.

5.4.3 *Comprehensive metabolic panel (CMP)*

A CMP will consist of determinations of sodium, potassium, chloride, bicarbonate, blood urea nitrogen (BUN), glucose, creatinine, aspartate transaminase (AST), alanine transaminase (ALT), alkaline phosphatase, lactate dehydrogenase, total bilirubin, total protein, albumin, serum calcium, magnesium, and phosphorous.

5.4.4 *Urinalysis*

Urinalysis will include pH, specific gravity, and hemoglobin, glucose, ketones, and protein by dipstick, with microscopic exam if any of the dipstick analytes are 2+ or higher.

5.4.5 *PSA*

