5.8 Criteria for Removal from Protocol Treatment

Every effort should be made to keep subjects on study drug for a minimum of 9 weeks (i.e., 3 cycles) unless withdrawal of informed consent, the presence of significant toxicity, clear progression of neoplastic disease, or any other reason for the removal from study as outlined in this section. Per the PCWG2 guidelines, "in the absence of clinically-compelling indicators of disease progression, early changes (within 9 weeks) in indicators such as serum PSA, patient-reported pain, and radionuclide bone scan should be ignored". With respect to bone scan changes, 72% of the apparent disease progressions, in the abiraterone acetate plus prednisone vs. placebo plus prednisone registration trial, proved to be responders and were able to continue therapy. In contrast, unequivocal signs of disease progression such as spinal cord compression or pain requiring a change in therapy would require discontinuation of Sacituzumab Govitecan prior to 9 weeks (i.e., before completing Cycle 3).

Subjects who require palliative radiotherapy for focal symptom relief may remain on study as long as the treating investigator feels they are deriving benefit from Sacituzumab Govitecan 2 and the radiotherapy is not to a target or non-target lesion recorded at baseline.

Subjects may be removed from protocol treatment under the following conditions:

- First documentation of progressive disease or symptomatic deterioration indicating treatment failure.
 - Discontinuation is subject to the goal of not removing subjects prior to completing 9 weeks of treatment especially for the lone reason of rising PSA. Subjects with rising PSA may continue on study beyond Cycle 3 at the discretion of the investigator.

- Subjects who want to continue treatment after radiological documentation of progressive disease should notify the physician who will obtain Sponsor approval before treatment continuation.
- Unacceptable toxicity, or any AE, which in the opinion of the investigator precludes further participation in the study.

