⁷All subjects should have adverse events evaluated at least 30 days from the last dose of study drug. Follow-up for progression will be performed every 3 months or per standard of care for up to 2 years from initiation of study therapy if subjects discontinue study treatment prior to progression. For subjects coming off-treatment due to progression, follow-up is complete once AEs have been evaluated at least 30 days after the last dose of the study drug.

⁸If not performed within 30 days of End of Treatment/Progression

⁹If lab values are not within normal range on day 1 or day 8, consider repeat CBC with differential on day 15, as per MD discretion. In the case of a Grade 3 ANC subjects should be assessed weekly and for grade 4 ANC subjects should be assessed bi-weekly as per section 6.4.1.

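### Sections 4, 5.8 and 8.2 do not agree on whether PSA-only progression after week 9 ends treatment, and the follow-up and censoring text carries that ambiguity into the 6-month rPFS co-primary

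*Combined protocol and SAP*

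**What the plan says.** **Stopping treatment**
- Section 8.2: "Treatments can continue until radiographic disease progression, unacceptable toxicity, initiation of alternative therapy or withdrawal of consent".
- Section 4: "Treatment with Sacituzumab Govitecan can continue until disease progression, unacceptable toxicity, initiation of alternative therapy or withdrawal of consent". The type of progression is not given. Elsewhere the same section requires that men at entry "have demonstrated disease progression (objective or PSA) while on second generation AR-directed therapy".
- Section 5.8 lists as a ground for removal: "First documentation of progressive disease or symptomatic deterioration indicating treatment failure". It discourages removal before 9 weeks for a rising PSA alone, then adds "Subjects with rising PSA may continue on study beyond Cycle 3 at the discretion of the investigator". It also provides for treatment past a radiographic event: "Subjects who want to continue treatment after radiological documentation of progressive disease should notify the physician who will obtain Sponsor approval before treatment continuation".

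**Follow-up and analysis**
- Section 5.3: "Subjects will undergo repeat evaluations of their extent of disease every 9 weeks", while the man is progression-free on study.
- Section 5.7: after treatment ends, men who have not progressed are assessed three-monthly or by local practice, until progression or another treatment. The type of progression is again not stated.
- Appendix B, footnote 7: "For subjects coming off-treatment due to progression, follow-up is complete once AEs have been evaluated at least 30 days after the last dose".
- Section 8.4.3: the 6-month rPFS rate is a Kaplan-Meier estimate using PCWG2 criteria. The censoring rule (last assessment) is written under median rPFS. Appendix E, which summarises PCWG2, contains a PSA progression criterion.

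**The concern.** Take a man with confirmed PSA progression at week 12 and stable scans. Under section 8.2 he has not reached the limit of treatment. Under section 4 he may have, if progression there includes PSA. Under section 5.8 the investigator decides.

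Stopping the drug is not itself an rPFS event, so the discrepancy matters only if stopping changes how the event is observed. The follow-up text makes that possible in two ways, which pull in opposite directions:
- If the stop is recorded as due to progression, footnote 7 closes follow-up and the man is censored. If PSA progression signals an approaching radiographic event, that censoring is informative and the estimate tends to be too high.
- If a site or analyst reads PCWG2 progression to include PSA, the same man becomes an rPFS event and the estimate is too low.

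The trial has one arm and fixed benchmarks of 20% and 40%, so no control group would absorb differences between sites.

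**Working it through.** **1. The plan's own figure.** Section 8.3 states 87% power for 20% versus 40% with 45 evaluable men at one-sided 0.025. The normal approximation gives Φ{[(0.40 − 0.20)√45 − 1.96√(0.2×0.8)] / √(0.4×0.6)} = Φ(1.14) = 87.3%. The exact test (success if at least 15 of 45) has alpha 0.02499 and power 85.7%. The figure is reproduced, and nothing below alters it.

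**2. What happens to a PSA-only stopper after week 9**

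| Reading | Later scans | rPFS status |
|---|---|---|
| Stays on drug (8.2; one option in 5.8) | Every 9 weeks | Followed to radiographic event |
| Stops, counted as not progressed (5.7) | Three-monthly or local practice, until progression or other treatment | Event or censored later |
| Stops, counted as progressed (footnote 7) | None scheduled after the End of Treatment visit | Censored at last assessment |
| Stops, PSA counted under PCWG2 | Not needed | Event |

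The documents do not say which of the last three rows applies.

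**3. Illustration A (all inputs assumed; the documents give no PSA-to-scan lag).** Radiographic time T is exponential with rate −ln(S)/182 per day, where S is the true 6-month rate. PSA progression occurs at T × Uniform(0.5, 1.3). A man is eligible to stop if his PSA time is before T and after day 63. Events are recorded at the next 9-week scan, stoppers are censored at their last scan, and Kaplan-Meier is read at day 190.

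| True rate | None stop | Half stop | All stop | None to all |
|---|---|---|---|---|
| 20% | 18.7% | 21.3% | 26.3% | +7.6 |
| 30% | 28.4% | 32.0% | 38.0% | +9.6 |

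The first column sits below the true rate because the last scan read is at 3 × 63 = 189 days: 0.20^(189/182) = 18.8% and 0.30^(189/182) = 28.6%. When all eligible men stop, 22–23% of all men stop for PSA alone before day 182; when half do, about 11%.

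Changing one assumption at a time (none to all, percentage points):

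| Variant | Shift |
|---|---|
| As above | about +7 to +10 |
| One scan 30 days after stopping, read at day 190 | about +3.5 to +5 |
| No scan after stopping, read at day 182 | about +2 to +4 |
| One scan 30 days after stopping, read at day 182 | about −3 |
| PSA timing unrelated to T, no scan after stopping | about −2 |

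The sign can reverse for two reasons. At day 182 the third scheduled scan (day 189) has not happened, so an extra scan after stopping brings forward events that would otherwise be dated day 189. When PSA timing is unrelated to T, censoring back to the last scan discards time in which the man was known to be event-free.

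**4. Illustration B (a different model, also assumed).** PSA progression comes first, between week 9 and month 6, in 20–40% of men. It multiplies the radiographic hazard by 1 to 3. Every such man stops and is censored then, with no later scan.

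| True rate | Share 20%: ratio 1 / 1.5 / 2 / 3 | Share 40%: ratio 1 / 1.5 / 2 / 3 |
|---|---|---|
| 20% | 19.9 / 22.6 / 24.4 / 26.7% | 20.3 / 25.3 / 28.6 / 33.9% |
| 40% | 39.9 / 42.1 / 43.5 / 45.9% | 40.3 / 44.0 / 47.2 / 51.6% |

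With a ratio of 1 there is essentially no bias. The extreme corner is 33.9 − 20 = +13.9 points. If PSA progression is instead counted as an event, a true 40% reads as about 12–31%.

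**5. Scale.** With 45 men the binomial standard error is √(0.2×0.8/45) = 6.0 points at 20% and √(0.3×0.7/45) = 6.8 points at 30%. In Illustration A, half of the eligible men stopping moves the estimate by 21.3 − 18.7 = 2.6 or 32.0 − 28.4 = 3.6 points.

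**The case against.** The strongest reply is that the sections can be read together. All three are worded permissively. Section 5.8 is the dedicated removal section and deals with PSA directly: hold to 9 weeks, then use discretion, with radiographic progression as the outer limit unless the sponsor agrees to go on. On that reading nothing obliges a site to stop for PSA alone. This stands in part. It rules out saying that sites will stop men at different times, but discretion still means that they may.

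A reader might also infer that section 4 defines on-study progression to include PSA. It does not. The phrase about objective or PSA progression describes failure of prior AR-directed therapy for eligibility. The stopping sentence in section 4 is unqualified, which is an ambiguity and not a PSA rule.

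On the endpoint, the name and the glossary call rPFS radiological, which favours excluding PSA-only events. Section 5.6 and Appendix B footnote 8 also provide an End of Treatment scan if none was done within 30 days, and section 5.7 continues assessments for men who have not progressed. These points weaken the route to bias but do not close it. Section 8.4.3 cites PCWG2 criteria without excluding PSA, and neither section 5.7 nor footnote 7 says which type of progression ends follow-up.

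**Conclusion.** The inconsistency is real, and the passages must be reconciled. It can affect the 6-month rPFS co-primary through scanning, censoring and the event definition.

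A reader might infer a 7 to 10 point upward bias. The documents do not support that. It requires every eligible man to stop, no scan after stopping, a read-out just after the day-189 scan, and PSA timing closely tied to radiographic timing. Across the variants of Illustration A the shift runs from about −3 to +10 points. Illustration B runs from about zero to +14 at its harshest corner, which pairs a 40% share with a threefold hazard. A mix of sites shifts the estimate less, and the half-stopping shift is smaller than one standard error. Neither sign nor size can be settled from the documents, because they give no PSA-to-scan lag.

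The PSA response co-primary is largely protected: it is read by week 9, and section 5.8 discourages earlier stopping for PSA alone.

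**What to change.** - Reconcile sections 4, 5.8, 8.2 and Appendix B footnote 7 to one statement on whether PSA-only progression after week 9 ends treatment, and have the other places cite it. Which clinical rule applies is for the sponsor to decide.
- In section 8.4.3, state that PSA-only progression is not an rPFS event, if that is the intention.
- In section 5.7 and footnote 7, state that a PSA-only stop counts as not progressed for follow-up, so that the scans already scheduled there continue to radiographic progression or another treatment.
- Record PSA-only stops under their own reason code in the eCRF.
- Add a sensitivity analysis of the 6-month rPFS rate that counts a PSA-only stop before any radiographic event as an event. Label it a worst-case bound and not a replacement endpoint, since it turns rPFS into a composite and can read far below the radiographic rate.

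The cost is a wording change in a few sections, one reason code and one extra analysis. Investigators may lose some discretion, and men who would otherwise be closed out under footnote 7 would have a few more follow-up scans.

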8.3 Determination of Sample Size

The primary endpoints for the study are (1) PSA response rate, which is defined as the proportion of subjects achieving a $\geq 50\%$ decline in PSA at or within 9 weeks of starting Sacituzumab Govitecan. Prior published data from retrospective studies report PSA response rates ($\geq 50\%$ decline) in 20-30% of subjects on 2nd line AR directed therapy after progression on a 1st line agent in the pre-docetaxel setting (3-8), (2) and the 6-month rPFS rate. The response rate appears higher with cytotoxic chemotherapy. Although data are limited in the pre-docetaxel setting, retrospective studies in the post-docetaxel setting suggest patients with prior response to abiraterone are more likely to respond to second line enzalutamide (9-11). The familywise type I error for the two primary endpoints of the study is one-sided 0.05 and a Bonferroni adjustment for evaluating two primary endpoints will be applied that each endpoint will be tested at the one-sided 0.025 (0.05/2) significance level. A PSA response rate of 20% or less will be considered as unacceptably low. A PSA response rate of 40% or more, on the other hand, will be considered sufficient evidence to consider further clinical trial investigation. Hence, the null hypothesis that the PSA response rate is 20% will be tested against the alternative hypothesis that the PSA response rate is 40%. A sample size of 45 evaluable subjects for PSA response (defined as subjects who received at least 1 dose of Sacituzumab Govitecan and have at least 1 post-dose assessment of PSA) is required to detect an increase in the PSA response rate from 20% to 40% with 87% power at the one-sided exact test with a significance level of 0.025. Analogously, a 6-month rPFS rate of 20% or less will be considered as unacceptably low and 40% or more considered sufficient evidence. Again a sample size of 45 evaluable subjects (for assessing 6-month PFS rate) is required to detect an increase in the 6-month rPFS rate from 20% to 40% with 87% power at the one-sided 0.025 significance level. The following table shows the probabilities for rejecting the null hypothesis with a sample size of 45 evaluable subjects, assuming that the true PSA response/6-month rPFS rates range between 35-50%.

Table 10. Attainable power levels with a sample size of 45 evaluable subjects

True PSA response/6-months PFS rate	Probability of rejecting null hypothesis
35%	68%
40%	87%
45%	96%
50%	>99%

Hence, a sample size of 45 evaluable subjects will provide between 68-99% power to detect a true PSA response rate or 6-month rPFS rate between 35-50% at the one-sided 0.025 significance level.

A sample size of 45 subjects will also be adequate for estimating toxicity rates with sufficient accuracy. Specifically, toxicity rates will be estimated with a standard error of less than 8% and the corresponding 95% confidence intervals will be no wider than 30%.

In order to account for unevaluable (for assessing PSA response or 6-month rPFS rate) subjects, 55 subjects in total will be enrolled.

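### Fixed Bonferroni at 0.025 per primary endpoint is valid, but Holm's step-down procedure keeps the same familywise 0.05 and gives the second endpoint more power if 46 to 55 subjects are evaluable

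*Combined protocol and SAP*

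**What the plan says.** Section 8.3 states that "The familywise type I error for the two primary endpoints of the study is one-sided 0.05", and divides it equally: "a Bonferroni adjustment for evaluating two primary endpoints will be applied that each endpoint will be tested at the one-sided 0.025 (0.05/2) significance level". Neither 8.3 nor 8.4 lets a success on one endpoint release its share of the error to the other.

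Both endpoints are set up as 20% against 40%. For PSA the plan claims a result "with 87% power at the one-sided exact test with a significance level of 0.025", based on 45 evaluable subjects. For rPFS, "a 6-month rPFS rate of 20% or less will be considered as unacceptably low and 40% or more considered sufficient evidence", and "Again a sample size of 45 evaluable subjects (for assessing 6-month PFS rate) is required", with the same 87% power at 0.025. The word exact is used for PSA only. To cover unevaluable subjects, "55 subjects in total will be enrolled".

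Section 8.4.3 gives a Wilson 95% interval for PSA response, and a Kaplan-Meier estimate with a two-sided 95% interval for the 6-month rPFS rate. It names no test for rPFS and no interval transformation.

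**The concern.** Under the fixed split, each endpoint is judged at 0.025 whatever the other shows. Holm tests the smaller p-value at 0.025 and, only if that is rejected, the other at 0.05. The familywise guarantee is the same, and every Bonferroni rejection is also a Holm rejection.

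What is at stake is the second claim. If one endpoint succeeds and the other has a one-sided p-value between 0.025 and 0.05, the present rule calls the other a failure although the familywise limit does not require it. With success counts this small, that band corresponds to one subject's outcome.

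**Working it through.** **Inputs (8.3).** Null rate 20%, target 40%, familywise one-sided 0.05, 0.025 per endpoint, 45 evaluable, 55 enrolled. Evaluable n is therefore examined from 45 to 55, with the same n for both endpoints.

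**1. The plan's own figure.** The one-sample normal approximation is

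power = Φ{[(p1 − p0)√n − z√(p0(1 − p0))] / √(p1(1 − p1))}.

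At n=45, z=1.96: (0.20 × 6.708 − 1.96 × 0.40) / 0.4899 = 1.138, so power is 87.2%. The same formula gives 67.9%, 96.4% and 99.3% at 35%, 45% and 50%, in line with Table 10. The exact test at n=45 needs 15 successes (attained level 0.02499) and has 85.7% power. The stated 87% is reproduced closely enough for this point.

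**2. Exact pass marks.** For each n, r(α) is the smallest r with P(X ≥ r | n, 0.20) ≤ α, and power is P(X ≥ r | n, 0.40). Write a for power at 0.025 and b for power at 0.05.

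| n | r at 0.025 | r at 0.05 | attained level at second step | a | b | b − a (points) |
|---|---|---|---|---|---|---|
| 45 | 15 | 15 | 0.0250 | 85.7% | 85.7% | 0 |
| 46 | 16 | 15 | 0.0304 | 80.8% | 88.1% | 7.3 |
| 47 | 16 | 15 | 0.0366 | 83.7% | 90.1% | 6.4 |
| 48 | 16 | 15 | 0.0437 | 86.3% | 91.9% | 5.6 |
| 49 | 17 | 16 | 0.0256 | 81.6% | 88.5% | 6.9 |
| 50 | 17 | 16 | 0.0308 | 84.4% | 90.4% | 6.1 |
| 51 | 17 | 16 | 0.0368 | 86.8% | 92.1% | 5.3 |
| 52 | 17 | 16 | 0.0436 | 88.9% | 93.5% | 4.6 |
| 53 | 18 | 17 | 0.0259 | 85.0% | 90.8% | 5.7 |
| 54 | 18 | 17 | 0.0310 | 87.3% | 92.4% | 5.0 |
| 55 | 18 | 17 | 0.0367 | 89.3% | 93.7% | 4.4 |

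Differences are taken before rounding. At n=45 a mark of 14 is not available, because P(X ≥ 14) = 0.0521. At a true 35% the corresponding gain for n=46 to 55 is 9.4 to 11.8 points.

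**3. From conditional to unconditional.** Column b applies only after the other endpoint has been rejected at 0.025. If both true rates are 40% and the endpoints are independent (an assumption), per-endpoint power under Holm is a + a(b − a):

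- n=46: 0.8078 + 0.8078 × 0.0729 = 86.7%
- n=50: 0.8439 + 0.8439 × 0.0606 = 89.5%
- n=55: 0.8934 + 0.8934 × 0.0435 = 93.2%

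**4. Both endpoints succeed.** Under independence, Bonferroni gives a² and Holm gives a² + 2a(b − a):

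- n=46: 65.3% to 77.0% (about 12 points)
- n=50: 71.2% to 81.4% (about 10 points)
- n=55: 79.8% to 87.6% (about 8 points)

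Under perfect dependence with equal rates the two counts coincide. Either both reach the 0.025 mark or neither does, so the gain is 0.

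**5. At least one endpoint succeeds.** Holm's first step is the Bonferroni test, so this probability is identical under the two procedures.

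**6. Error control.** If both nulls are true, Holm makes a first false rejection exactly when Bonferroni does. If only one is true, it is falsely rejected with probability at most the attained level in the table, 0.0256 to 0.0437 for n=46 to 55. Neither argument uses independence, which matters because both endpoints come from the same patients.

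**The case against.** The strongest reply is that nothing here is wrong. The plan states the familywise level, the method and the per-endpoint level, and sizes each endpoint to match. The design size is 45, where the exact test gains nothing, and the extra ten subjects are there to absorb losses. Holm does not change the chance that this single-arm phase II trial finds a signal; it adds only a second formal claim. All of that stands, and it is why this is an optional improvement. More than 45 evaluable is nevertheless realistic for PSA: 8.3 asks for one dose and one post-dose PSA, and Appendix B schedules a PSA at Cycle 1 Day 8.

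Four stronger readings are tempting, and the documents do not support them:

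- **That Bonferroni is an error.** It is not; it controls the stated 0.05.
- **That rPFS gains even at 45, through a log-log Kaplan-Meier interval whose mark would fall from 15 to 14.** Section 8.4.3 names no such interval. With complete follow-up, passing at 14 of 45 has true size 0.0521, above 0.05.
- **That 80.8% to 88.1% is the overall power gain at n=46.** It is conditional on the other endpoint's success; the unconditional value under independence is 86.7%.
- **That the chance of double success rises by 12 points.** That is the independence figure. PSA response and rPFS in the same patients are plausibly positively related, and the gain shrinks to zero at perfect dependence.

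A reporting objection also stands. A two-sided 95% interval corresponds to one-sided 0.025, so an endpoint rejected at 0.05 may have an interval that includes 20%. The Wilson lower limit is 19.95% at 15/48 and 19.91% at 16/52, both of which pass at the second step.

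**Conclusion.** The point holds as a missed efficiency of low severity. Holm gives the same familywise protection and never rejects less. At every evaluable size from 46 to 55 the exact pass mark for the endpoint tested second falls by one. At a true 40% this is worth 4.4 to 7.3 points of power conditional on the first rejection, and somewhat less unconditionally.

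The result rests on the following:

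- the exact binomial test is used, and both endpoints have the same evaluable n;
- more than 45 subjects are evaluable, since at 45 the gain is zero;
- for rPFS, no subject is censored before 6 months, because otherwise the Kaplan-Meier estimate is not a simple proportion and the exact figures do not carry over;
- for the unconditional and double-success figures, independence, with zero gain in double success at the opposite extreme of perfect dependence and equal rates.

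**What to change.** Before the primary analysis, replace the Bonferroni sentence in 8.3 with:

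> Holm's step-down procedure at familywise one-sided 0.05 will be used, with the endpoint with the smaller p-value tested at 0.025 and, if rejected, the other at 0.05.

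The sample-size statement at 0.025 can stay, since the first step is still made at that level.

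Add to 8.4.3 that the two-sided 95% intervals are for estimation, and that an endpoint rejected at 0.05 is also reported with its one-sided 95% bound (the lower limit of a two-sided 90% interval).

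The cost is two short text changes, with no extra subjects and no loss of error control. The small downside is that the second endpoint's 95% interval may include 20% although its test rejects. The trial is open-label and the monitoring committee sees cumulative responses twice a year (9.4.2), so the change should be dated and documented ahead of the analysis.

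### PSA response power with 45 evaluable subjects is stated as 68% (true rate 35%) and 87% (true rate 40%), but the named one-sided exact test gives 64.7% and 85.7%

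*Combined protocol and SAP*

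**What the plan says.** Section 8.3 sets two primary endpoints, PSA response rate and 6-month rPFS rate, and splits a one-sided familywise error of 0.05 between them, so that "each endpoint will be tested at the one-sided 0.025 (0.05/2) significance level". For PSA response the null rate is 20% and the alternative is 40%. The plan says that a sample of 45 evaluable subjects "is required to detect an increase in the PSA response rate from 20% to 40% with 87% power at the one-sided exact test", at significance level 0.025.

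Table 10, titled "Attainable power levels with a sample size of 45 evaluable subjects", applies to both endpoints. It lists power of 68%, 87%, 96% and >99% at true rates of 35%, 40%, 45% and 50%. The paragraph after the table says that "a sample size of 45 evaluable subjects will provide between 68-99% power to detect a true PSA response rate or 6-month rPFS rate" over that span of true rates.

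The exact test is named only in the PSA response sentence. The rPFS sentence gives the same 87% without naming a test, and Section 8.4.3 estimates the 6-month rPFS rate by Kaplan-Meier.

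**The concern.** A one-sided exact binomial test has only whole-number cutoffs, so at 45 subjects its power can take only certain values. The 68% and 87% are not among them: no cutoff at 45 gives that pair. The text therefore names one method while the figures fit another.

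At stake is the accuracy of the power claimed for a primary endpoint. The plan also calls 45 subjects the number required for 87% power with this test, and 45 subjects do not give that. Someone reading Table 10 would put the chance of missing a true 35% response rate at 32% and of missing a true 40% rate at 13%. Both are too low.

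**Working it through.** **Inputs, all from Section 8.3.** Null rate p0 = 0.20; design alternative 0.40; n = 45 evaluable; one-sided level 0.025; one-sided exact test for PSA response; true rates of 35%, 40%, 45% and 50% from Table 10. No outside assumption is needed.

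**Step 1: reproduce the plan's figures.** The one-sample normal approximation without continuity correction, with the null variance setting the cutoff, is

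power = Φ[ (p − p0 − 1.96 × √(p0(1−p0)/n)) / √(p(1−p)/n) ].

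The null standard error is √(0.20 × 0.80/45) = 0.05963, and 1.96 × 0.05963 = 0.1169.

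- p = 0.35: (0.15 − 0.1169)/0.0711 = 0.466, power 67.9%
- p = 0.40: (0.20 − 0.1169)/0.0730 = 1.138, power 87.3%
- p = 0.45: (0.25 − 0.1169)/0.0742 = 1.795, power 96.4%
- p = 0.50: (0.30 − 0.1169)/0.0745 = 2.457, power 99.3%

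All four round to the Table 10 entries. The documents do not name the formula, so the source is inferred from the match. Three other common approximations do not give the pair at 35% and 40%: continuity-corrected 62.2% and 83.8%; arcsine 62.3% and 84.3%; variance under the alternative only 56.0% and 78.2%.

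**Step 2: find the exact cutoff.** The test rejects at r or more responders, where r is the smallest whole number with P(X ≥ r) ≤ 0.025 for X ~ Binomial(45, 0.20).

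- P(X ≥ 14) = 0.0521, above 0.025
- P(X ≥ 15) = 0.02499, allowed

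The cutoff is 15 of 45.

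**Step 3: exact power, P(X ≥ 15) for X ~ Binomial(45, p).**

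| True PSA response rate | Stated | Exact test, cutoff 15 | Stated minus exact (points) |
|---|---|---|---|
| 35% | 68% | 64.7% | 3.3 |
| 40% | 87% | 85.7% | 1.3 |
| 45% | 96% | 95.9% | agrees as rounded |
| 50% | >99% | 99.2% | agrees |

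**Step 4: look for another rule that would rescue the figures.** A cutoff of 14 gives 75.6% and 91.6% at true rates of 35% and 40%, but its size is 0.0521. A cutoff of 16 gives 52.5% and 77.5%. Requiring the lower limit of the two-sided 95% Wilson interval in Section 8.4.3 to exceed 20% again leads to 15: the limit is 19.5% at 14/45 and 21.4% at 15/45. A score test and a mid-p test also give 15.

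**Why the two methods differ.** The approximation rejects above a proportion of 0.20 + 0.1169 = 0.3169, which is 0.3169 × 45 = 14.26 responders. The real rule has to wait for 15.

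**Type II error.** The exact test misses a true 35% rate with probability 100 − 64.7 = 35.3%, against the 32% implied by Table 10. At 40% it is 100 − 85.7 = 14.3%, against 13%.

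**Sample size for 87%.** With the exact test at 0.025, power at a true rate of 40% first reaches 87% at 52 evaluable subjects (88.9%); 51 give 86.8%.

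**The case against.** The arithmetic is not open to dispute; the case against concerns weight and reading. At the 40% design alternative, the only rate for which the running text claims power by the exact test, the gap is 1.3 points and the trial still has about 86% power. The larger gap lies in the 35% row, and Table 10 names no test and serves rPFS as well; a common approximation would be understandable for a shared table. Attainable in the table title may mean no more than achievable. Exact power at 40% also moves between 80.8% (46 evaluable) and 89.3% (55 evaluable) as the evaluable number varies within the 55 enrolled, so 1.3 points is small beside that.

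Most of this stands as a limit on importance. Applying the exact test to the table's 35% row is an inference, but a natural one: the table expressly covers PSA response, follows the exact-test sentence and repeats its 87%. The mismatch does not depend on how the title is read. The variation with the evaluable number does not make 87% or 68% correct at 45, the number for which they are stated.

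**Conclusion.** The PSA response power figures at true rates of 35% and 40% are wrong as written for the test the plan names. The exact one-sided test at 0.025 with 45 evaluable subjects gives 64.7% and 85.7%, so power is overstated by 3.3 and 1.3 points. The 45% and 50% rows are correct as rounded. The result rests only on inputs stated in Section 8.3 and on reading the exact test as applying to the PSA response side of Table 10. It does not extend to rPFS. The error is minor: it does not invalidate the choice of 45 evaluable subjects and leaves alpha and the hypotheses as they are.

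**What to change.** In Section 8.3:

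- For PSA response, state 86% power at a true rate of 40% with the one-sided exact test at 0.025, rejecting at 15 or more of 45 (attained size 0.02499).
- Give Table 10 a separate PSA response column: 65%, 86%, 96%, >99%.
- In the paragraph after the table, give the PSA response range as 65-99%.
- Leave the rPFS figures as they are, and have the sponsor confirm the method behind them.

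A shorter alternative is to say that the tabulated figures come from a normal approximation. The 87% should then no longer be attributed to the exact test, and the exact 86% should be given for PSA response.

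Optional, and separate from the error: state that the exact test at the actual evaluable number decides the PSA endpoint (cutoff 15 at 45 subjects, 16 at 46-48, 17 at 49-52, 18 at 53-55) and that the Wilson interval in Section 8.4.3 is descriptive.

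The cost is wording and one table column. The sample size need not change; the stated PSA power becomes slightly less favourable.
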